4.1. Inclusion criteria

1/ Signed Informed consent

2/ Patients should be intermediate 1 or low according to IPSS with at least one poor prognosis feature

- MDS classified according to revised IPSS at least intermediate
- □ RBC transfusion dependent anemia and failure to 2 lines of therapy if eligible (including EPO, Lenalidomide or demethylating agents ...) with the exception of pure RARS with isolated SF3B1 mutation
- thrombocytopenia < 20 G/L requiring transfusion

- □ neutropenia < 0.5 G/L associated with severe infection (defined as requiring hospitalization)
- 5q- and lenalidomid failure especially but not only with TP53 mutated

$3/ \text{Age} \ge 18 \text{ and} < 70 \text{ years}$

For young patients, 18-45 years, Fanconi disease and dyskeratosis should be ruled out by standard test in order to test frequent constitutional genetic alteration.

4/ Patient for whom a transplantation from a matched donor, (8/8 (HLA A, B, C, DRB1) identical at molecular level) unrelated donor or matched sibling), is considered irrespective of donor availability

5/ Performance status 0-2 on the Eastern Cooperative Oncology Group (ECOG) Scale (at time of screening)

6/ Negative pregnancy and adequate contraception (including in male patients wishing to father), if relevant

7/ Wash-out of at least 30 days since a previous treatment with Vidaza[®], Lenalidomide, EPO or any other treatment inducing cytopenias

4.2. Exclusion criteria

1/ MDS classified according to classical IPSS as intermediate 2 or High risk

2/ Transformation in Acute Myeloid Leukemia (AML)

3/ ARSI SF3B1 mutated

4/ Severe active infection or any other uncontrolled severe condition

5/ Organ dysfunctions including the following:

- Hepatic: total bilirubin > 2 times upper limit of normal (ULN) (except moderate unconjugated hyperbilirubinemia due to intra medullary hemolysis or Gilbert syndrome), alanine transaminase (ALT) and aspartate transaminase (AST) > 3xULN
- Symptomatic respiratory chronic failure
- Symptomatic cardiac failure
- Renal clearance < 60 ml/min

6/ Prior malignancy (except in situ cervix carcinoma, limited basal cell carcinoma, or other tumors if not active during the last 3 years)

7/ MDS with the following causal germline disease : Fanconi anemia, GATA2 related syndromes and telomere disorders.

Any patient with family history of hematologic disorder and/or dysmorphic syndrome (skeletal malformation ; nail, skin or hair abnormalities ; cardiac abnormalities, growth restriction, pulmonary or hepatitis fibrosis) which

suggest a germline causal mutation of the hematological disease, should send a skin biopsy and blood samples (5 tubes 5 ml with EDTA) to [name] at Saint-Louis Hospital.

4.3. Discontinuation criteria

All patients will be followed at least 2 years after the date of the last inclusion according to each center policy and disease status (transformation in a higher risk MDS, especially AML) and death (date and cause) will be collected until the end of the protocol and for a maximal duration of 5 years.

5. Number of patients and study duration

- The trial will enroll **105** patients, 62 in group A (donor), 43 in group B (no donor), over a 36-month period
- The whole study will be performed over a 5-year period

6. Therapeutic procedures

Patients will be assigned to group A or B (donor or no donor) after at least 2 months after inclusion to allow the time for donor search.

6.1. Group A: Patients with a donor

- Iron chelation

Patients with iron overload defined as more than 20 blood cell transfusions (since initial diagnosis) or ferritin level > 1000 ng/mL will start Exjade® at 20 mg/kg per day of deferasirox dispersible tablets or 14 mg/kg per day of deferasirox film-coated tablets (when converting a patient from deferasirox dispersible tablets to deferasirox film-coated tablets, the dosage should be decreased by 30%) or will continue Exjade® if they were receiving it before inclusion at a minimal dosage of 20 mg/kg of deferasirox dispersible tablets or 14 mg/kg of deferasirox film-coated tablets or same dose if they were receiving a higher dose. Exjade® will be temporarily discontinued one day before conditioning regimen start or at any moment in case of renal failure (clearance < 60 ml/min). In those patients, Exjade® will be restarted on day 100 in patients with LIC > 5 mg Fe/gr dry weight (defined before the transplantation), except in cases of contraindications including gastro-intestinal disorder (nausea, vomiting, abdominal pain or diarrhea), renal failure (clearance < 60 ml/min), active GVHD, neutropenia < 0.5 G/L, thrombocytopenia < 30 G/L, total bilirubin, AST, ALT > 2xULN, GGT and PAL > 3xULN.

Before restarting Exjade[®], complete iron measurements will be repeated (serum iron, serum ferritin, transferrin saturation, NTBI, LPI, hepcidine) and MRI.

The initial dose of Exjade[®] after transplant will be 10 mg/kg/day of deferasirox dispersible tablets or 7 mg/kg per day of deferasirox film-coated tablets progressively increased to 20 mg/kg/day or 14 mg/kg/day respectively if good tolerance.

Patients with iron overload will be evaluated at each visit by serum ferritin, transferrin and iron in serum; will be evaluated 12 months after transplant by complete iron measurements including serum iron, serum ferritin, transferrin saturation, NTBI, LPI and hepcidine.

Hepcidine and non-transferrin binding iron will be measured in the ancillary biological study (Hôpital Louis Mourier, see appendix 10).

As soon as ferritin reached a level < 700 ng/mL, Exjade[®] will be discontinued.

- Transplantation (D0)

The HSCT should be **scheduled 4 months after the inclusion** either with an HLA-matched sibling or a 8/8 (A,B,C,DRB1) HLA matched unrelated donor.

Preferable source of stem cells will be granulocyte colony-stimulating factor-mobilized peripheral blood stem cells (PB), in case of donor refusal, marrow could be accepted. Minimal CD34+ cells requested will be 3×10^6 /kg body weight recipient or 2×10^8 /kg body weight recipient (before in vitro manipulation).

- GVHD prophylaxis

GVHD prophylaxis will consist in Cyclosporine on day -1 (per os: 2.5 mg/kg twice a day, with a target residual between 100 and 300) plus Mycophenolate Mofetil (Cellcept®). Mycophenolate Mofetil on day +1 (15 mg/kg twice a day) will be tapered from day 30 to day 45 or stopped when corticosteroids are started to treat an acute GVHD. In the absence of GVHD, Cyclosporine will be progressively tapered from day 120, 25% per 2 weeks until total discontinuation.

D-5	D-4	D-3	D-2	D-1	D0	D+1	D+
					HSCT		
-	-	-	-	Start Cyclosporine	-	Start MMF	D+30 to D+45:
				2.5 mg/kg		(Cellcept®) 15 mg/kg	Stop progressively MMF
				twice a day		twice a day	
							Since D+120:
							Stop progressively
							Cyclosporine (-25%

			per	2	weeks	until
			total discontinuation			ation

- Conditioning regimen

 Conditioning regimen will be as followed 	-	Conditioning	regimen	will be	as followed
--	---	--------------	---------	---------	-------------

-	D-5	D-4	D-3	D-2	D-1	DO
FLUDARABINE mg/m ²	30	30	30	30	30	-
IV BUSULFAN mg/kg	-	-	3.2	3.2	-	-
ATG-FRESENIUS (GRAFALON) mg/kg	-	-	10	10	10	-
CORTICOSTEROIDES mg/kg	-	1	2	2	2	-

Administration of conditioning regimen will follow the following procedure:

- Usual nausea-vomiting prevention
- Hyperhydratation is not required
- Fludarabine will be injected by central venous catheter in 30 minutes
- Busulfan will be injected by central venous catheter in 3 hours once daily or in 2 hours fourth a day

- ATG-Fresenius (GRAFALON) will be preceded by corticosteroides and 5 mg polaramine[®] or equivalent antihistaminic. **Heparin should not be administrated during ATG-Fresenius (GRAFALON) administration.** ATG-Fresenius (GRAFALON) will be injected by central venous catheter in 12 hours the first day and 8 hours the second and third day with surveillance of temperature, tension, and pulse every 30 minutes; in cases of hypotension, the perfusion should be discontinued until recovery and restarted at lower velocity.

Anti-infectious prophylaxis

According to national and European guidelines, all patients will received a prophylaxis for herpes simplex (acyclovir or valacyclovir), pneumocystis and toxoplamosis (sulfametoxazole/trimethoprime or sulfadoxine/pyrimethamine or atovaquone) except during aplasia, anti-fungal therapy (fluconazole).

All patients will be monitored for CMV and EBV reactivation by weekly PCR in blood until the third month.

No engraftment

If the patient has acute or late rejection with persistent of severe pancytopenia, a second transplant has to be discussed. The quicker this second transplant is performed, the best chance the patient has to avoid severe infection. According to performance status and comorbidities, a second transplant with same or different donor can be re-scheduled as soon as possible, if possible no later than 3 weeks after rejection diagnosis.

If the patient has an autologous reconstitution with good or moderate hematological reconstitution, or returns to his baseline count, a second allogeneic transplant is not recommended until the disease progresses.

Management of immunosuppressive treatment and donor lymphocyte infusion

As reported in the regimen schema, Mycophenolate Mofetil will be decreased from day 30 and stop on day 45 while Cyclosporine will be decreased on day 120, 25% per 2 weeks in absence of acute GVHD. The optimal dosage of Cyclosporine between D0 and D120 will be between 150 and 350 ng/ml when intravenous and a residual > 150 ng/ml (< 350) when oral route.

There is no systematical preventive donor lymphocyte infusion in this trial (because patients are at low risk).

In some cases, immunosuppressive therapy can continued later if the patient presents acute GVHD until acute GVHD has resolved.

In other cases, if there are some evidences of disease activity and / or mixed chimerism after day 30, immunosuppressive treatment will be discontinued earlier (except if active GVHD). Patients should be evaluated 6 weeks after immunosuppressive discontinuation and in cases of persistence mixed chimerism and/or disease activity proven by marrow analysis, DLI should be planned (at least 6 weeks after immunosuppressive discontinuation) except if the patient had a previous grade II to IV acute GVHD or in patients with active chronic GVHD. The donor can be collected to have a set of 4 donor lymphocytes packages which can be infused in the recipient as follow:

-first: 1x10⁶ CD3+ cells /kg

-second: 0.5x10⁷ CD3+ cells /kg

-third: 1×10^7 CD3+ cells /kg

-fourth: 0.5x10⁸ CD3+ cells /kg.

Each DLI will be injected after a minimum interval of 6 weeks and immediately stopped in cases of GVHD occurrence. A combined treatment with Vidaza[®] is also accepted, particularly in the patients with blast excess. In these cases, hypomethylating agents will be used according to their approval (Autorisation de Mise sur le Marché).

If the patient is 100% recipient chimerism, there is no indication to perform DLI. DLI can be done later if the patient has some donor cells (mixed chimerism or donor chimerism) after treatment.

Other treatment: If the transplantation is not performed for any reasons

Patients can benefit from any treatment including phase II prospective studies, or a treatment considered as the best available treatment. There are no unapproved medications which are tested in this trial.

If the disease evolves to a higher risk by acquiring new cytogenetic abnormalities, new cytopenia or an increase in marrow blast including a transformation into AML, a transplant using an alternative donor should be considered (mismatch unrelated donor, unrelated cord blood or mismatch related donor including haploidentical transplant), if possible in the setting of a trial assessing alternative transplant.

6.2. Group B: Patients without a donor

- Iron chelation

[figure not shown]
Iron chelation will be started if baseline ferritin level > 1000 ng/L or in those receiving more than 20 RBC units (or continued if they already received it). Exjade[®] will be started at 20 mg/kg per day of deferasirox dispersible tablets or 14 mg/kg per day of deferasirox film-coated tablets (when converting a patient from deferasirox dispersible tablets to deferasirox film-coated tablets, the dosage should be decreased by 30%) or will continue if they were receiving it before inclusion at a minimal dosage of 20 mg/kg of deferasirox dispersible tablets or 14 mg/kg of deferasirox film-coated tablets.

- Other treatment

Patients can benefit from any treatment including phase II prospective studies, or a treatment considered as the best available treatment. There are no unapproved medications which are tested in this trial.

If the disease evolves to a higher risk by acquiring new cytogenetic abnormalities, new cytopenia or an increase in marrow blast including a transformation into AML, a transplant using an alternative donor should be considered (mismatch unrelated donor, unrelated cord blood or mismatch related donor including haplo-identical transplant), if possible in the setting of a trial assessing alternative transplant.

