1.3.2. Treatment of iron overload

Chelating agents have demonstrated that they were efficient for iron depletion. A large prospective study testing deferasirox in 1744 MDS patients receiving chronic RBC transfusions for various reasons reported that serum ferritin and NTBI was decreased under treatment but 66% suffered from reversible adverse events (gastro-intestinal symptoms, skin rash, increase in serum creatinine) requiring dose reduction^{50,51}.

10

A more specific study on lower risk MDS patients reported also a normalization of NTBI in all patients but treatment discontinuation mainly due to gastro-intestinal disturbances. Deferasirox reduces serum ferritin and labile plasma iron in RBC transfusion-dependent patients with myelodysplastic syndrome⁵².

Except from biological changes with iron chelation agents, it has been also reported that iron chelation itself can induce haematological improvement in MDS patients^{53,54}.

Concerning improvement of quality of life, one prospective study in MDS transfused patients failed to demonstrate the role of chelation agents⁵⁵ but no controlled randomized studies comparing chelation versus placebo are available.

In the setting of transplant, conflicting studies exist reporting an excess of non-relapse mortality in patients with a high ferritin level or who received massive transfusion while prospective studies give conflicting results (see above) failing to demonstrate an association between liver iron overload and post-transplant mortality^{56,57}.

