8.1. At inclusion

After checking the inclusion and exclusion criteria, as well as parameters necessary for stratification, the investigator will request inclusion online.

The following information will be collected:

- Medical history: date of diagnosis and initial disease characteristics (blood counts, bone marrow results, cytogenetic analysis)
- Previous treatments and history of RBC and platelet transfusions

Then, the investigator will:

- Check inclusion criteria
- For young patients, 18-45 years, contact [name] by e-mail ([contact])

- Collect the informed consent (clinical +/- biological study)
- Perform clinical examination: weight, height, PS (ECOG, Appendix 1), co-morbidity (Appendix 2-3)
- Perform baseline blood tests including: full blood count and differential, including peripheral blasts count and reticulocytes, AST, ALT, serum bilirubin, LDH, PAL, GGT, creatinine, EPO level, CRP, B12 and folates test
- Urine test: proteinuria
- Perform bone marrow aspiration for morphology, cytogenetics, and correlative biological studies (2 mL EDTA). If this analysis has been done within the 2 months prior to inclusion and if peripheral blood cell counts are stable: a new bone marrow aspiration could be avoided if BM sample have been sent to the CHRU of Lille, [name] laboratory, and SMD molecular analysis have already been performed (ASXL1, TP53, EZH2, ETV6, RUNX1...)
- Send bone marrow (2 ml EDTA) and blood (10 ml EDTA) samples for molecular analysis
- Send serum, 10 ml (2 tubes 5 ml without EDTA or citrate), before Exjade[®] initiation, to Louis Mourier Hospital for iron biological study
- HLA will be performed in these patients and in their siblings (if available and age < 70 years without cancer, thrombosis or cardiac failure history). If no donor is available among siblings, a matched unrelated donor 8/8 unrelated donor is searched. Antibodies against HLA should also be checked.
- Iron overload will be estimated at registration by the number of transfusions received since initial diagnosis, iron parameters (serum iron, transferrin saturation, serum ferritin)
- **Heart and liver MRI** should be performed within 6 weeks in patients with iron chelation criteria: ferritin level > 1000 ng/mL (can be done also before inclusion, maximally 6 weeks before)
- Pregnancy test, if applicable
- Quality of life questionnaire (EORTC)

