8.2. Visits

For all enrolled patients, visits will be performed:

- at inclusion
- every two weeks during the first 4 weeks (first month)
- every 4 weeks from the 5th week to the 26th week (until 6th month)
- every 8 weeks from the 27th week to the 52th week (until 12th month)
- every 12 weeks from the 53th week to the end of study.

At each patient visit, the following information will be registered:

- Grade III to IV adverse events (classified according to NCI- CTCAE 4.0) http://evs.nci.nih.gov/ftp1/CTCAE/CTCAE_4.03_2010-06-14_QuickReference_5x7.pdf

- Treatment by Exjade[®] and its dose
- Clinical assessment (every 2 weeks on first month)
- Weight, PS, serious infectious disease (defined in Appendix 4)
- Transfusion history (platelet and RBC) including the research of allo-immunisation (RAI)
- AST, ALT, serum bilirubin, serum creatinine, PAL, LDH, GGT, CRP

- Proteinuria (rapid urine test)

- Pregnancy test, if applicable
- Blood cell count including reticulocytes (every week during the 1th month then every 4 weeks)
- Ferritin level, transferrin level and saturation, plasmatic iron level
- In case of disease progression/relapse suspicion, marrow + cytogenetic analysis

Specific information for specific point (after inclusion):

- Quality of life questionnaire (EORTC) at 12, 24 and 36 months

- Centralized biological study (hepcidine, LPI, NTBI): At 3 and 16 months after inclusion (specific form in Appendix 10)

- **Bone marrow aspiration** with cytogenetic (local laboratories) and molecular biology (CHRU Lille) will be performed according to local policy but at least once a year

For patients who received a transplant:

- Pre-graft tests including cardiac assessment and respiratory assessment with pulmonary tests

- **Centralized biological study (hepcidine, LPI, NTBI):** just before conditioning regimen (D-5), just before transplant on day 0, and on day 7, 30, 100, 365 post-transplant

- Between 2 to 3 months after the transplant, a **bone marrow aspiration** (with shipment for biological study: BM 2 ml EDTA)

- At least one post-transplant **chimerism** in blood after engraftment on day 30. The chimerism will be repeated only if the first one is not donor > 95% or in cases a rejection is suspected

- Acute GVHD grade per organ at each visit (Appendix 6)

- Neutrophil engraftment and platelet engraftment (within 60 days post-transplant)

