8.3. Diary8.3.1. Diary for transplanted patient (Group A)

8.3.2.	Diary for NON-Tran	planted patient	(Group B)
--------	---------------------------	-----------------	-----------

Time from registration	D0 Screening	D30 M1	D60 M2	D90 M3	D120 M4	D150 M5	D180 M6	D240 D365 M8- M12	D365 D990 M12-M33	D1080 M36
Inform consent	х									
Clinical visit	x	X2/ M	x	х	x	x	x	X Every 2 months	X Every 3 months	x
Comorbidity assessment	x			x						
ECOG	х	х	х	х	х	х	х	х	х	х
Blood cell counts (9)	x	X1/ W	X1/M	X1/M	X1/M	X1/M	X1/M	X1/M	X1/M	X1/M
Standard biology (1)	х	х	х	х	х	х	х	х	х	х
EPO, folates, B12	х									
Iron plasmatic dosage (2)	x	x	x	x	x	x	x	x	x	x
HLA typing (3)	х	х	х							
Centralized biological study (4)	Х*			x					M16	
Proteinuria	х	х	х	х	х	х	х	х	х	х
Bone marrow aspiration + blood + cytogenetics (5)	x								M12 &24	x
Heart and liver MRI (6)	x			x						
QOL	x								M12 & 24	x
AE Grade III-IV	x	x	х	х	x	x	x	x	x	х

(1) Every visit: Proteinuria, AST, ALT, serum bilirubin, serum creatinine, PAL, LDH, GGT, CRP

(2) Serum ferritin, transferrin, iron plasmatic level

(3) HLA A, B, C, DRB1 molecular level

(4) Centralized study – 2 tubes without EDTA 5 mL to Louis Mourier Hospital, see specificity in appendix 10. *Before Exjade initiation (5) Inclusion, D60 to D100 post-transplant or once a year for non-transplant patient. Including cytogenetic and centralized shipment

for molecular analysis to CHRU Lille (BM 2 ml EDTA + Blood 2 tubes 5 mL with EDTA)

(6) Only for patients with SF > 1000 ng/mL or more than 20 RBC transfusions at time of inclusion. At time of screening, could be done within 6 weeks before or after inclusion. *After transplant, should be done at D100 and before Exjade restarting

(7) Include cardiac and pulmonary assessment

(8) Assessment at D30. *Should be repeated at the next visits only if the first one is not donor > 95% or in cases a rejection is suspected

(9) Including reticulocytes and blast count

9. Statistical analysis

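### Section 6.2 prints the group B ferritin trigger for chelation in ng/L where the rest of the protocol uses ng/mL, and its text does not repeat the renal hold for Exjade (minor correction)

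*Protocol*

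**What the plan says.** Two sections govern iron chelation with Exjade.

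- **Section 6.1 (group A, donor).** Patients with "more than 20 blood cell transfusions (since initial diagnosis) or ferritin level > 1000 ng/mL will start" Exjade, at 20 mg/kg of dispersible tablets or 14 mg/kg of film-coated tablets. The drug is stopped temporarily one day before conditioning, or "at any moment in case of renal failure (clearance < 60 ml/min"). It is stopped for good once ferritin falls below 700 ng/mL.
- **Section 6.2 (group B, no donor).** "Iron chelation will be started if baseline ferritin level > 1000 ng/L or in those receiving more than 20 RBC units". The starting doses are the same as in 6.1. Patients already on Exjade continue at no less than those doses. The chelation text ends there.

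The same ferritin criterion appears elsewhere in ng/mL. Section 8.1 asks for heart and liver MRI "in patients with iron chelation criteria: ferritin level > 1000 ng/mL". Footnote 6 to the diaries in section 8.3, repeated in Appendix 11, limits MRI as follows: "Only for patients with SF > 1000 ng/mL or more than 20 RBC transfusions at time of inclusion". Section 3.2 defines iron overload at the same ng/mL value.

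On renal function, section 4.2 excludes patients at entry with "Renal clearance < 60 ml/min". Section 8.2 has these tests recorded at each visit for all enrolled patients: "AST, ALT, serum bilirubin, serum creatinine, PAL, LDH, GGT, CRP".

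**The concern.** The first matter is a wrong unit in the sentence that decides treatment. Read literally, the ferritin trigger in 6.2 could not serve as a threshold for iron overload, and the instruction contradicts the rest of the protocol, including the footnote that applies to group B's own visit schedule.

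The second is a gap between two sections that give the same drug at the same starting dose. The protocol itself identifies the risk: section 1.3.2 reports a large deferasirox study in which "66% suffered from reversible adverse events (gastro-intestinal symptoms, skin rash, increase in serum creatinine") and needed dose reduction. It sets a limit of 60 ml/min, monitors creatinine in everyone, and writes down the action for group A only. At stake are clear instructions and the safety of chelated group B patients whose renal function declines on study. The trial's statistical conclusions are not at stake.

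**Working it through.** **Unit of the trigger**

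Inputs: 1000 ng/L (section 6.2); 1000 ng/mL (sections 3.2, 6.1, 8.1 and footnote 6); stop level 700 ng/mL (section 6.1).

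- Conversion: 1000 ng/L ÷ 1000 mL per L = 1 ng/mL.
- Ratio to the threshold used elsewhere: 1000 ng/mL ÷ 1 ng/mL = 1000.
- Ratio to the level at which 6.1 stops the drug: 700 ng/mL ÷ 1 ng/mL = 700. Taken literally, group B would start chelation at a ferritin 700 times below the level at which group A stops it.

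The places side by side:

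| Place | Applies to | Ferritin criterion |
|---|---|---|
| 3.2 Secondary objectives | both groups | > 1000 ng/mL |
| 6.1 | group A | > 1000 ng/mL |
| 6.2 | group B | > 1000 ng/L |
| 8.1 At inclusion | all, before groups exist | > 1000 ng/mL |
| Footnote 6, section 8.3 and Appendix 11 | MRI row of both diaries | > 1000 ng/mL |

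The entry for 6.2 is the only one out of line among statements that direct treatment or assessment. The background (section 1.3.1) prints ng/L once, when it reports a meta-analysis, but directs nothing there. Since ng/mL prints correctly everywhere else, the simplest explanation is a typing slip in the source.

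**Renal hold**

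No arithmetic applies. The question is whether any other text supplies for group B what 6.1 supplies for group A.

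- Section 4.2 has the same 60 ml/min limit, but at entry only. It does not cover a later fall.
- Section 8.2 measures creatinine and records the Exjade dose at each visit, but attaches no action to a result.
- Sections 10.1 and 10.3 ask for the action taken on adverse events and whether treatment was suspended. These are recording duties, not dosing rules.
- Section 10.2 refers to the product characteristics to define expected events, not to manage doses.

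None of these states a hold for group B.

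Timing suggests that one common rule was intended, though this is an inference. Section 6 assigns patients to a group at least 2 months after inclusion. Section 6.2 triggers chelation on baseline ferritin, and section 3.2 assesses chelation at 3 months in all patients. Many patients would therefore start before their group is known, when neither 6.1 nor 6.2 yet applies by name.

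**Number affected**

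The documents do not say how many group B patients will be chelated, so no estimate is possible. The planned group B size of 43 (section 5) is the whole group, not the chelated part.

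**The case against.** The strongest case against the first point is that it is copy-editing. Section 8.1 gives every site the right value at inclusion, footnote 6 repeats it for group B, and any haematologist would see that 1 ng/mL cannot be meant. This largely stands and is why the point is minor. It does not make the sentence right, and the correction costs almost nothing.

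Against the second point there are four arguments.

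- A figure belongs to the chelation part of 6.2 or to the trial design heading in 6.3, and its content was not available. If it carries a dosing rule, the gap may not exist. This stands, and it limits the claim to the running text.
- The hold in 6.1 sits in a transplant sequence of conditioning, interruption and restart at day 100, which group B does not have, so the difference could be deliberate. This is possible, but the renal clause applies at any time and does not depend on transplantation.
- Investigators would probably suspend the drug anyway, and the reporting forms expect that they may. This also stands. The gap is one of written instruction, not of monitoring.
- Section 6.2 also lacks the 700 ng/mL stop level of 6.1, so adding only the renal hold is selective. That difference is real, and the sponsor may wish to consider it in the same amendment. It concerns when treatment has done its work, however, whereas the hold protects the patient.

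A reader might infer more: that group B will be chelated at almost any ferritin, that its patients are meant to stay on Exjade as renal function falls, or that the two groups are managed so differently that the survival comparison is biased. The documents support none of these. The correct unit appears in all the other operative places, nothing tells investigators to continue below 60 ml/min, and no effect on any analysis can be shown.

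**Conclusion.** The unit in section 6.2 is wrong as printed: 1 ng/mL instead of 1000 ng/mL, a factor of 1000. Confidence in this is high, because it rests only on comparing the text and converting the unit. The practical effect is probably small, on the assumption that sites read the value as ng/mL.

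The missing renal hold is a secondary point held with lower confidence. It assumes that the unread figure does not state the hold and that the sponsor did not intend different renal rules for the same drug and starting dose.

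Both are minor corrections. The primary survival comparison, the sample size and the other analyses are unaffected, and the number of patients concerned is unknown.

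**What to change.** 1. In section 6.2, change the unit of the ferritin threshold from ng/L to ng/mL.
2. State the renal hold for group B in the terms of 6.1: Exjade is suspended whenever clearance falls below 60 ml/min. Alternatively, put the start threshold and the hold once in a short common paragraph before 6.1, valid for every chelated patient from inclusion. The common paragraph is tidier, since it also covers the weeks before group assignment. If the figure in 6.2 already states the hold, only the first change is needed.

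The cost is one unit and one sentence, which can go with the next amendment. Creatinine, ferritin, weight and the Exjade dose are already recorded at each visit under section 8.2, so no new visit, test or data field is required.
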